2. Applying a waterproof film dressing (e.g. Ioban®, which is a betadine impregnated adhesive dressing) over the wound for one week.
3. Postoperative intravenous antibiotic prophylaxis dictated by local policy.
4. Placing the wound drain *in situ* on gravity (rather than suction) for one week.
5. We discourage use of Tisseel glue, which is widely used in neurosurgery to reduce CSF leak, because this product expands and may thus itself cause spinal cord compression.
6. Sitting up the patient to >45° for a week to reduce cervical CSF pressure.
7. Removing the sutures at two weeks.
8. Suturing the dural patch to dura, rather than merely applying the duroplasty without suturing it.
9. Sutures to tighten the skin around the probes to reduce CSF leak (mechanistic studies).

The above measures will be discussed with the surgeons at each participating site and will be part of the online training course for participating centres but will not be imposed. Patient management will be left to the local clinical teams. These data will be documented in the CRF.

RISKS OF ISP AND MD MONITORING: In 2018, we published the safety profile of injury site monitoring for up to a week in a cohort of 42 AIS A – C TSCI patients (including cervical and thoracic injuries) treated at St. George's Hospital in London (Table below). The most common complications are CSF related and easy to manage by adding extra sutures to the wound or spontaneously resolve. These findings suggest that injury site monitoring in TSCI patients is a safe technique.

COMPLICATION	PATIENTS NO.	%	COMMENTS
CSF leak	3 / 42	7	Resolved by wound re-suturing
Wound infection or breakdown	0 / 42	0	
Meningitis (septic)	0 / 42	0	
Pseudomeningocele	8 / 42	19	All resolved at 6 month MRI
Probe displacement	1 / 42	2	
Neurological deterioration	0 / 42	0	
Haematoma	0 / 42	0	

TRIAL SAFETY: DISCUS will run in accordance with OCTRU's Standard Operating Procedures (SOPs) and operational policies, which adhere to all applicable UK regulatory requirements. The trial will be overseen by a DSMC and a TSC. The project will also be monitored by the sponsor (City St George's, University of London).

The DISCUS trial is categorised as:

- ~~Type A = No higher than the risk of standard medical care~~
- ~~Type B = Somewhat higher than the risk of standard medical care~~
- ~~Type C = Markedly higher than the risk of standard medical care~~

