C	Motor Incomplete	Motor function is preserved at the most caudal sacral segments for voluntary anal contraction OR the patient meets the criteria for sensory incomplete status by light touch, pin prick or deep anal pressure, and has some sparing of motor function more than three levels below the ipsilateral motor level on either side of the body. <50 % of key muscle functions below the level of injury have muscle grade ≥ 3 .
D	Motor Incomplete	Motor incomplete as defined above, with ≥ 50 % of key muscle functions below the neurological level of injury having muscle grade ≥ 3 .
E	Normal	Sensation and motor function graded as normal in all segments.

SECONDARY OUTCOMES (FUNCTION):

4. CUE-Q (to assess upper limb function) at 6 months.
5. Hand grip strength using a dynamometer at 6 months.
6. WISCI-II (to assess walking ability) at 6 months.
7. SCIM-III (to assess self-care and daily living) at 6 months.

SECONDARY OUTCOMES (QUALITY OF LIFE):

8. SF-36 at 6, 12 months.

4. – 8. are standardised tools. We will use these functional scales, which are established in TSCI, to confirm that the motor improvement that we seek is associated with functional improvements: CUE-Q (hand function), grip strength, WISCI II (walking) and SCIM III (independence measure that includes sphincter function and validated in TSCI). In addition, we use one a HRQoL scale as a secondary outcome measure (SF-36,) aiming to show that the functional improvement translates to improvement in HRQoL.

SECONDARY OUTCOMES (SAFETY)

9. Number of re-operations required on the spine within 12 months
10. Total length of hospital stay (Stay in MTC, stay in spinal injury unit, other hospital admissions)
11. Surgical complications and adverse events – recorded postoperatively and at follow-up visits
12. Overall survival (OS) – time from randomisation to death or end of follow-up (1 year)
13. MRI 2 weeks: Size of pseudomeningocele
14. MRI 6 months: Spinal deformity (Cobb angle between superior C2 and inferior C7 endplates); Size of pseudomeningocele,

9. – 12. are objective measures that yield the same value independent of assessor. 14. (spinal deformity) Is a standardised tool. Safety of duroplasty will be assessed in different ways, not only by comparing complications and adverse events, but also by determining the number of re-operations on spine, total hospital stay, OS as well as spinal deformity in the duroplasty versus the non-duroplasty arms.

SECONDARY OUTCOMES (MECHANISM):

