15. MRI at 2 weeks (all patients):

- a. Length of cord compression (no CSF around the cord in mid-sagittal MRI)

16. MRI at 6 months (all patients):

- a. Length of cord tether
- b. Length of cord syrinx

17. Pressure monitoring at injury site (mechanistic study patients):

- a. Mean daily ISP
- b. Mean daily SCPP

18. MD monitoring at injury site (mechanistic study patients):

- a. Mean daily metabolites (glucose, lactate, pyruvate, LPR, glutamate, glycerol)
- b. Mean daily cytokines (GRO α , IL1 α , IL1 β , IL4, IL8, IL10, IP10, MCP1, MIP1 α , MIP1 β) or others.

15. and 16. are not standard measures because they are particular for DISCUS and will be measured on MRI by two radiologists. 17. and 18. are objective measures independent of assessor. The aim is to determine the mechanism by which duroplasty improves outcome. We will investigate if dural + bony decompression more effectively decompresses the swollen cord than bony decompression alone, i.e. lower ISP, higher SCPP, CSF around injured cord (MRI). More effective decompression by duroplasty is predicted to improve spinal cord metabolism, compared with bony decompression alone, i.e. more energy (higher glucose), less ischaemia (lower lactate, higher pyruvate and lower LPR), less excitotoxicity (lower glutamate) and less cell death (lower glycerol). More effective decompression by duroplasty is also predicted to reduce cord inflammation, compared with bony decompression alone, i.e. lower GRO α , IL1 α , IL1 β , IL4, IL8, IL10, IP10, MCP1, MIP1 α , MIP1 β . In the long-term (6 months), the extra space created by duroplasty is predicted to reduce cord tethering at the injury site and spinal cord syrinx.

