Imaging assessments: MRI and CT images will be transferred by image exchange portal (IEP) or otherwise to St. George's Hospital for analysis. The preoperative CT is done **before the patient has entered DISCUS** as part of standard of care. DISCUS does not request for this CT to be done but, if the scan is available as standard of care, then DISCUS will use some information from this scan. IEP is a web-based application that allows healthcare professionals to securely transfer patient images from one hospital to another. NHS and private hospitals have been using IEP since January 2010. Transfer of images by IEP is the preferred method of image transfer rather than CD to maximise data protection and improve patient management by ensuring the images are from the PACS (Picture Archiving and Communication System) of the source hospital to the PACS of the destination hospital. PACS is the standard medical imaging technology used to securely store and digitally transmit electronic images and clinically relevant reports that eliminates the need to manually file and store, retrieve and send sensitive information, films and reports. Pre-operatively, we will record cause of injury, level of injury, surgical approach and type of injury (as per AO sub-axial classification system A, B, C, F to be done by the neuroradiology P.I. based on CT). From the MRI done within 2 weeks of surgery, we will note how well the cord is decompressed i.e. the length of cord on T2 mid-sagittal view without CSF in front and behind it as well as size of pseudomeningocele. We will measure the cranio-caudal (height), antero-posterior (length) and medio-lateral (width) lengths of the pseudomeningocele using the T2 sagittal and axial MRI sequences, and estimate its volume as (height x width x length / 2). It is vital to record MRI features at 6 months including cord tethering (i.e. whether there is CSF around the cord) to the surrounding dura which is expected to reduce with duroplasty as more space is created around the cord as well as size of pseudomeningocele to be determined as described above.

A major problem with TSCI patients is delayed syrinx formation and therefore the size of syrinx (cranio-caudal length on T2) will also be assessed using the 6 month MRI. Finally, we will assess deformity at 6 months to make sure that duroplasty does not lead to kyphosis.

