9.3 Operational definitions for (S)AEs

The following will be reported by site as an SAE reportable to the central team within 24 hours:

- Death: only if deemed potentially directly related to duroplasty or probes (for example meningitis from CSF leak).
- Meningitis (defined as fever + symptoms/signs of meningism + elevated CSF neutrophil count and positive CSF microbiology culture)

- Redo spinal surgery: only if deemed potentially directly related to duroplasty or probes (e.g. repair of CSF leak, removal of retained probe)
- Worsening of AIS grade: only if deemed potentially directly related to duroplasty or probes
- Wound infection that requires antibiotics: only if deemed potentially directly related to duroplasty or probes
- Wound breakdown that requires surgical debridement: only if deemed potentially directly related to duroplasty or probes (i.e. wound breakdown from deep infection)

EVENTS EXEMPT FROM BEING REPORTED AS SAEs

The following are complications and collected as outcome and do not require SAE reporting:

- Death: related to reasons other than duroplasty or probes (e.g.: *deaths related to pulmonary embolus*)
- Repair of CSF leak not requiring general anaesthetic (e.g. *Lumbar drain insertion, Re-suturing of wound of probe site*)
- Redo spinal surgery unrelated to duroplasty or probes (e.g. *evacuation of haematoma, surgery for: Metalwork failure, Deformity correction, Removal of metalwork, Syrinx*)
- Worsening of AIS grade (*If deemed NOT related to duroplasty or probes, this does not need reporting and will be picked up in 6-month ISNCSI/assessment*)

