17. APPENDICES

17.1 Appendix 1 - Risk

Risks associated with trial interventions

- A ≡ Comparable to the risk of standard medical care
- B ≡ Somewhat higher than the risk of standard medical care
- C ≡ Markedly higher than the risk of standard medical care

JUSTIFICATION: The RCT involves performing a duroplasty that carries a small risk as detailed below. Insertion of the pressure and MD probes intradurally also carries a small risk. Therefore, the study is classed at B.

What are the key risks related to therapeutic interventions you plan to monitor in this trial?		How will these risks be minimised?		
Intervention	Body system/Hazard	Activity	Frequency	Comments
Duroplasty	1. CSF leak 2. Wound infection 3. Meningitis (septic) 4. Pseudomeningocele	1. Wound re-suture / lumbar drain 2. Ioban, Antibiotics 3. Antibiotics 4. No treatment, spontaneously resolves	1. Once / 5 days 2. 1-2 weeks 3. 1-2 weeks 4. N/A	1-3) Reducing CSF leak also reduces risk of wound infection and meningitis. Use of nylon sutures for skin closure, which are more watertight than staples. Apply a waterproof film dressing (e.g. Ioban®, which is a betadine impregnated adhesive dressing) over the wound for one week.
ISP / MD monitoring	1. CSF leak 2. Wound infection 3. Meningitis (septic) 4. Pseudomeningocele 5. Probe displacement 6. Neurological deterioration 7. Haematoma	1. Wound re-suture / lumbar drain 2. Ioban, Antibiotics 3. Antibiotics 4. No treatment, spontaneously resolves 5. Disconnect when moving patient 6. Insert probe under microscope 7. Insert probe under microscope, Haemostasis	1. Once / 5 days 2. 1-2 weeks 3. 1-2 weeks 4. N/A 5. Each time 6. Once 7. Before closure	Placing the wound drain on gravity (rather than suction) for a week. Sit up patient to >45° for a week to reduce cervical CSF pressure. Remove the sutures at two weeks. Suture dural patch to dural edges, rather than merely apply the duroplasty without suturing it. Sutures to tighten skin around probes to reduce CSF leak. 4) Pseudomeningocele spontaneously resolves 6-7) The probes are inserted under microscope and advanced parallel to the cord

[figure not shown]
Should surgical complications / adverse events above that typically expected be reported, these will be reviewed by the Data Safety and Monitoring Committee (DSMC).

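### Section 9.3 uses haematoma evacuation and deformity correction as examples of redo surgery unrelated to the interventions, although the protocol links haematoma to the probes and checks duroplasty for kyphosis; this invites misclassification at site

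*Protocol*

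**What the plan says.** Section 9.3 has two bullets on redo spinal surgery.

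- **Reportable within 24 hours:** "Redo spinal surgery: only if deemed potentially directly related to duroplasty or probes (e.g. repair of CSF leak, removal of retained probe".
- **Exempt from SAE reporting, collected as a complication:** "Redo spinal surgery unrelated to duroplasty or probes (e.g. *evacuation of haematoma, surgery for: Metalwork failure, Deformity correction, Removal of metalwork, Syrinx".

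Other sections bear on the same events.

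- Appendix 1 (17.1) tabulates the key intervention risks to be monitored. Its row for ISP and microdialysis monitoring ends "5. Probe displacement 6. Neurological deterioration 7. Haematoma", with mitigation given for each.
- Section 2.1 reports the "safety profile of injury site monitoring for up to a week in a cohort of 42 AIS A – C TSCI patients" and includes a haematoma line, with 0 of 42.
- Section 7.7 says "we will assess deformity at 6 months to make sure that duroplasty does not lead to kyphosis".
- Section 3.3 places deformity in the between-arm safety comparison, along with re-operations and "total hospital stay, OS as well as spinal deformity in the duroplasty versus the non-duroplasty arms".

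**The concern.** A definition of exempt events should turn on whether the event is related to the intervention. This bullet states that condition but illustrates it by type of procedure, and two of the types are ones the protocol elsewhere connects with its own interventions. A site returning a monitored patient to theatre for a haematoma will find that operation named on the exempt list and absent from the examples on the reportable list. The natural reading is that the question has already been answered.

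If the site follows the example and files no SAE form, three things do not happen: the report within 24 hours, the central expectedness review under 9.4, and the event's appearance on the SAE list. The DSMC reviews that list at every meeting, whereas it reviews other adverse events only on request (Roles and Responsibilities, Data and Safety Monitoring Committee). Probe insertion is an intradural procedure done for research, so its serious harms should reach that review reliably.

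**Working it through.** The point rests on the text, and the plan gives no figure to reproduce. The check has four steps.

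**1. Haematoma.** Section 9.3 offers haematoma evacuation as an example of surgery unrelated to duroplasty or probes. Appendix 1 names haematoma as a monitored probe risk, and section 2.1 counts it as a possible complication of monitoring. For a patient with probes these do not agree. For a patient without probes there is no conflict, because the duroplasty row of Appendix 1 lists only CSF leak, wound infection, septic meningitis and pseudomeningocele. The direct conflict is therefore confined to the mechanistic study, planned at 50 or more patients (sections 4 and 10.1).

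**2. Deformity.** Section 9.3 offers deformity correction as unrelated. Section 7.7 measures deformity because duroplasty might cause kyphosis, and section 3.3 makes it a safety outcome. This link is weaker: 7.7 describes a check rather than an attribution, and Appendix 1 does not list deformity as a duroplasty hazard. Still, something measured to see whether duroplasty causes it is a poor model of an unrelated event.

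**3. Drafting within 9.3.** The exemptions for worsening AIS grade, deep wound infection and wound breakdown each depend on the event being judged not related. The redo-surgery bullet states its condition as a description and then lists procedures. Section 9.2 asks for a graded causality judgement on each adverse event, and its lowest grade is reserved for events clearly not related. A list of procedures cannot stand in for that judgement.

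**4. What the monitoring series can exclude.** Inputs: 0 haematomas, n = 42 (section 2.1). With no events, the exact upper limit p solves (1 − p)^n = a, so p = 1 − a^(1/n).

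- One-sided 95%: 1 − 0.05^(1/42) = 0.0688, or 6.9%.
- Two-sided 95%: 1 − 0.025^(1/42) = 0.0841, or 8.4%.

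The observed rate is zero. The limits show only that the series is too small to rule out probe haematoma. They refer to any haematoma, not to one needing evacuation, and the protocol gives no figure for the latter. It gives no rate for deformity surgery either.

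**The case against.** The strongest reply is that the exempt bullet still carries its condition. The procedures are examples inside a class defined as unrelated, and the companion bullet makes the same surgery reportable when a relation is potential. Read strictly, evacuation of a haematoma at the probe tip fails the exempt condition and meets the reportable one. This stands. A reader might infer that such harms are exempt in advance, and the document does not support that.

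The safeguards are also real. Section 9.3 encourages sites to report when unsure. It sends exempt events to monthly TMG review and to assessment by clinicians unrelated to surgery. Section 9.2 asks for causality on every adverse event. Every spinal re-operation within 12 months is a safety outcome, and the DSMC also sees accrued data or summaries by arm. So the events are not lost and causality assessment is not bypassed. These safeguards narrow the gap without closing it. Advice to report when unsure does not help a site whose doubt a matching example has removed, and monthly review is not a 24-hour report. Probes go into both arms of the mechanistic study (section 2), so a comparison of re-operations between arms cannot be relied on to isolate a probe harm.

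Three further inferences are tempting and should not be drawn.

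- **Syrinx.** It is on the same example list, but the protocol never names it as a harm of duroplasty or probes. It says "the extra space created by duroplasty is predicted to reduce cord tethering at the injury site and spinal cord syrinx". No contradiction is shown.
- **SUSARs.** Section 9.1 reserves the term for reactions not listed as expected. Appendix 1 lists haematoma, so it is doubtful that a typical probe haematoma would qualify even if reported.
- **A patient count.** Multiplying 6.9% by the size of the mechanistic study would turn an upper limit for any haematoma into an apparent forecast of evacuations. The document does not support that.

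**Conclusion.** The point holds as a drafting inconsistency that invites misclassification at site. It is clear for haematoma in patients with probes and weaker for deformity correction. What is exposed is 24-hour reporting, expectedness review and the routine SAE list for the DSMC. Collection of the events, their monthly review and the count of re-operations are not affected.

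The number of patients is unknown and probably small. The only relevant figure is 0 of 42, with a one-sided 95% upper limit of 6.9% for any probe haematoma. Applying even that limit to this trial assumes that the cited cohort, which included thoracic injuries and monitoring for up to a week, resembles the trial's cervical patients monitored for up to 5 days. The conclusion also assumes that sites use the examples as a guide when classifying. The protocol cannot show whether they do, but that is the purpose of examples in an operational definition.

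**What to change.** Reconcile section 9.3 with sections 2.1, 7.7, 9.2 and Appendix 1. Either of two changes does this:

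1. Remove haematoma evacuation and deformity correction from the examples of unrelated redo surgery. The metalwork and syrinx examples can stay.
2. Reword the bullet so that redo surgery is exempt only if judged not related to duroplasty or probes, matching the deep-infection and wound-breakdown bullets.

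Under either, relatedness is judged case by case on the 9.2 scale, and the existing reportable bullet applies wherever a relation is potential. The cost is one wording change, a note to sites and possibly a few extra SAE forms. Treatment, endpoints and sample size are untouched.

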** Note: 5% of patients have unexplained worsening of AIS grade. **
- Deep wound infection that needs antibiotics if deemed NOT related to duroplasty or probes
- Wound breakdown that requires surgical debridement if deemed NOT related to duroplasty or probes
- Pseudomenigocele
- Pressure ulcers (during 1st week post op - outside this period no need to report)
- Readmissions to hospital

DISCUS collects all complications (adverse events – events exempt from being reported as SAEs). The investigators are encouraged to report an event as an SAE if unsure and contact the trial office. Events collected as complications from sites will be reviewed by the TMG monthly and assessed by team of clinicians unrelated to surgery.

Assessment and management of risk

Where possible, SAEs and SARs will be evaluated for duration and intensity e.g.: Lumbar drain insertion to treat CSF leak (no. of days), Meningitis (duration of antibiotics), Redo spinal surgery (duration of hospital stay), Worsening of AIS grade (grade), Wound infection that requires antibiotics (duration of antibiotics), Wound breakdown that requires surgical debridement.

Breaking the blind will only take place where information about the participant's trial treatment is clearly necessary for the appropriate medical or surgical management of the participant. We do not anticipate that breaking of the blind will be required for DISCUS.

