Assessment of complications: Complications will be recorded post-operatively and at clinic visits and will be monitored and reported by the sites. We will record at 6 and 12 months the number of re-operations on the spine to ensure that duroplasty does not lead to further operations related to CSF leak or wound infection, though based on known safety data, we think this is unlikely. We will also record the length of hospital stay, which may reduce if duroplasty is beneficial, but may be confounded by availability of rehabilitation beds. Adverse events and complications relating to surgery will be recorded and reported by the sites.

Mechanistic assessments: From the monitoring to be performed for up to 5 days after surgery, we will assess mean daily ISP, SCPP, glucose, lactate, pyruvate, LPR, glutamate and glycerol. As there is no

consensus or evidence on what are considered normal ISP/SCPP/metabolite values, it is not ethical to alter treatment based on these values.

We will explain this to PIs during site visits and in the training videos. Once metabolites have been measured on site, the MD vials will be coded by patient number and day from injury and stored at -20 °C and periodically shipped to [name] at City St. George's, University of London for analysis of inflammatory markers to compute mean daily GRO α , IL1 α , IL1 β , IL4, IL8, IL10, IP10, MCP1, MIP1 α and MIP1 β .

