9.4 Recording and reporting of SAEs, SARs AND SUSARs

All SAEs occurring from the time of written informed consent/ randomisation until 12 months post randomisation should be recorded on the SAE Report Form. Trial centres will use a standardised electronic SAE form to inform the Trial Manager of SAEs. All SAEs (other than those defined in this protocol as not requiring reporting) must be reported on the SAE reporting form on REDCAP .

The Trial Management Team will perform an initial check of the report and request any additional information from the site team. SAEs will also be reviewed at TMG meetings. DSMC and TSC will get a list of SAEs.

The 'causality', 'expectedness' and 'seriousness' of SAEs (i.e. relationship to trial treatment) will be assessed by the local investigator(s) on the SAE form. A clinician unrelated to surgery may be consulted on the SAE assessment. All SAEs, will be reviewed by the DISCUS Trial Manager and discussed with Chief Investigators to determine whether the SAE is "*related*" and "*unexpected*" as defined by the HRA guidance. These will then be assessed by the DISCUS Nominated Person.

The assessment of 'causality' by the local investigator will not be downgraded by the DISCUS Trial Office, even if the Nominated Person does not concur with the assessment. Under these circumstances both assessments will be recorded and causality deemed as 'related'.

For SAEs that require reporting, expectedness of SARs will be performed centrally by the Nominated Person for the trial and determined according to the Sponsor-.

The DISCUS Trial Office is responsible for reporting SAEs, where appropriate, to the Sponsor and REC within required timelines. An SAE occurring to a participant will be reported to the REC that gave a favourable opinion of the study where in the opinion of the Chief Investigators the event was 'related' (resulted from administration of any of the research procedures) and 'unexpected' in relation to those procedures.

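### Section 9.3 lists a wound infection at any depth if related to duroplasty or probes, but only a deep one if unrelated, so superficial infections are under-recorded mainly in controls

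*Protocol*

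**What the plan says.** Section 9.3 gives two lists. The first holds events that sites report as SAEs within 24 hours. It includes "Wound infection that requires antibiotics: only if deemed potentially directly related to duroplasty or probes" and "Worsening of AIS grade: only if deemed potentially directly related to duroplasty or probes". Section 9.4 sets the window: "All SAEs occurring from the time of written informed consent/ randomisation until 12 months post randomisation should be recorded on the SAE Report Form".

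The second list holds events exempt from SAE reporting and collected as complications. Its infection entry is "Deep wound infection that needs antibiotics if deemed NOT related to duroplasty or probes". For AIS worsening judged unrelated it says "this does not need reporting and will be picked up in 6-month ISNCSI/assessment". Section 9.3 then states: "DISCUS collects all complications (adverse events – events exempt from being reported as SAEs".

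Section 3.3 makes these data part of the safety comparison between arms: "Safety of duroplasty will be assessed in different ways, not only by comparing complications and adverse events". Appendix 1 names wound infection among the key duroplasty risks to be monitored.

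**The concern.** The second list should complete the first, so that the two together count every event of a given kind whatever its cause. For wound infection they do not, because the unrelated entry carries a depth limit that the related entry lacks.

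Attribution is tied to the arm. A control patient can have a related event only through a monitoring probe, and probes are optional (section 4 plans at least 25 such patients per arm). The narrower definition therefore applies to most controls, while a duroplasty patient with the same superficial infection can enter through the wider one. Equal true risk would then appear as a small excess on duroplasty. No analysis plan can repair this afterwards, because events that were never recorded cannot be recovered.

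**Working it through.** The plan gives no figure to reproduce. The check sets the wording side by side and then illustrates the size.

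**Wording**

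| Event | Judged related to duroplasty or probes | Judged unrelated |
|---|---|---|
| Wound infection needing antibiotics | any depth, SAE list | deep only, complications list |
| Worsening of AIS grade | any, within 24 hours, to 12 months | not reported by the site; left to the 6-month examination |

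The mismatch does not run through the whole list. Death and redo spinal surgery broadly mirror each other across the two lists, and meningitis is reportable whatever its attribution.

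**Inputs for the infection illustration**
- n = 111 per arm (222 randomised 1:1; sections 4 and 10.1).
- f = share of controls with probes: 25/111 = 0.225 (section 4 minimum), or 0.
- s = share of infections that are superficial: assumed 0.5, range 0.3 to 0.7.
- q = share of superficial infections attributed to duroplasty or probes, where attribution is possible: assumed 0.5, range 0.25 to 0.75.
- p = true risk, equal in both arms. It cancels from the ratio.

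**Formulas** (deep infections are captured in both arms; superficial ones only if attributed)
- Duroplasty, fraction captured: (1 − s) + s·q
- Control, fraction captured: (1 − s) + s·f·q
- Difference in expected counts: n·p·s·q·(1 − f), which is positive for any s, q > 0 and f < 1

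**Results**

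| s | q | Duroplasty | Control, 25 with probes | Control, none with probes | Ratio, 25 | Ratio, none |
|---|---|---|---|---|---|---|
| 0.3 | 0.25 | 0.775 | 0.717 | 0.700 | 1.08 | 1.11 |
| 0.5 | 0.5 | 0.750 | 0.556 | 0.500 | 1.35 | 1.50 |
| 0.7 | 0.75 | 0.825 | 0.418 | 0.300 | 1.97 | 2.75 |

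**Counts, central case with 25 probed controls**
- At p = 4/277 = 1.44 % (Chiari series, section 2.1): 111 × 0.0144 = 1.60 true infections per arm. Recorded: 1.60 × 0.750 = 1.20 against 1.60 × 0.556 = 0.89, a difference of about 0.3.
- At an assumed p = 5 %: 5.55 true infections per arm. Recorded: 4.16 against 3.09, a difference of about 1.1.
- The protocol's own spinal-injury series show 0/26 (duroplasty) and 0/42 (monitoring, infection or breakdown), so the rate may be lower still.

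**AIS worsening.** The 5 % unexplained worsening noted in section 9.3 is 0.05 × 111 = 5.55 patients per arm, but that is all such worsening, not the part at risk of being missed. Worsening still present at 6 months is captured in both arms by the secondary outcome on AIS grade (section 3.3). Section 11.1 says the AIS chart is normally also completed at discharge from the major trauma centre and transferred to the trial database. Section 7.4 puts that transfer at around 2–3 months. Appendix 2 schedules the assessment only at admission and month 6. What can be missed is unrelated worsening that resolves between charts or begins after 6 months. The documents give no figure for it.

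**The case against.** The strongest reply is that other passages already catch these infections. Section 7.7 says "Adverse events and complications relating to surgery will be recorded and reported by the sites", with no depth limit and no tie to duroplasty. Section 9.1 defines an adverse event without regard to relatedness, and Appendix 2 schedules a record of complications at day 14 and at months 3, 6 and 12. Section 9.4 requires every SAE not expressly exempted to be reported, so an unrelated superficial infection that is serious, for instance by prolonging the stay, returns to SAE reporting. Section 9.3 also encourages SAE reporting when in doubt.

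Part of this stands. The gap is confined to non-serious superficial infections, and sites that follow section 7.7 broadly may record some of them. But section 7.7 sets no definition, and section 9.3 equates complications with the exempt list, which is the narrow one. Section 9.4 also produces an odd inversion: a serious superficial unrelated infection must be reported as an SAE while a deep one is exempt.

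Three stronger readings are tempting and are not supported:
- **Unrelated AIS worsening is invisible until 6 months.** Section 11.1 describes a chart at discharge.
- **The spurious ratio is 2.0, or up to 4.** That comes from 1/(1 − s) with s = 0.5 or 0.75. It needs every superficial duroplasty-arm infection to be attributed and no control to have probes.
- **The case report form has no place for wound infection.** The postoperative items in section 7.6 include none, but section 7.7 refers to a list of procedure-specific complications whose form is not shown.

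**Conclusion.** The infection definitions in section 9.3 differ by attribution, and the shortfall falls mainly on controls. The direction, against duroplasty, follows from the wording if sites record from the two lists.

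The size rests on assumed shares. The recorded ratio is about 1.35 at equal true risk, with a range of 1.08 to 1.97 when 25 controls have probes and up to 2.75 when none do. With roughly 0.3 of an infection between arms at 1.4 %, a ratio on such counts says little by itself, although one or two unrecorded events could change how a sparse table reads. The AIS part comes down to a small, unquantified remainder and an inconsistency between sections. The severity is minor. The point is worth correcting because the change is nearly free and the loss cannot be undone at analysis.

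**What to change.** - **Infection.** Delete the word Deep from the exempt-list entry in section 9.3, so that both entries cover any wound infection requiring antibiotics. Record depth (superficial or deep) as a field in both arms. Compare infections between arms regardless of attribution.
- **AIS worsening.** Reconcile section 9.3 and Appendix 2 with section 11.1 on whether an AIS chart at discharge from the major trauma centre is a trial assessment, and use that chart in both arms. Do not ask sites to report worsening whenever it is noticed. Staff at the operating hospital may know the allocation, so ad hoc reporting could itself differ by arm.

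The cost is one deleted word, one form field and one reconciliation of sections. The downside is a few more low-grade entries for sites. Note the date of the change, since patients already followed up will have been recorded under the present wording.
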